3.2 Secondary Endpoints

[figure not shown]
- Secondary endpoints will include evaluation of the A) DLTs and other toxicities (as assessed by the NCI CTCAE v4.03), B) RP2D, C) antitumor activity (as assessed by the RECIST 1.1), and D) plasma PK and pharmacodynamics of the L-NMMA and pembrolizumab combination.

4.0 TRIAL DESIGN

4.1 Description of Trial Design

This is a Phase Ib trial assessing the safety of the pan-NOS inhibitor L-NMMA in combination with pembrolizumab in subjects with melanoma, NSCLC, HNSCC, cHL, urothelial carcinoma, cervical cancer, esophageal cancer, gastric cancer, hepatocellular carcinoma, merkel cell carcinoma, primary mediastinal large B-cell lymphoma, renal cell carcinoma, small cell lung cancer, MSI-H/dMMR cancer, or for the treatment of adult patients with unresectable or metastatic tumor mutational burden-high (TMB-H) [≥ 10 mutations/megabase (mut/Mb)] solid tumors. This trial will determine the MTD, DLTs and other toxicities, and RP2D of the L-NMMA and pembrolizumab combination and will utilize a standard Bayesian model averaging continual reassessment method (CRM) approach to determine the appropriate dose of L-NMMA (see Section 8.0 — Statistical Considerations). A cohort size of 2 will be used.

Figure 1. Study Diagram

5.0 METHODOLOGY

5.1 Entry Criteria

5.1.1 Diagnosis/Condition for Entry into the Trial

Female or male subjects ≥ 18 years of age with melanoma, NSCLC, HNSCC, cHL, urothelial carcinoma, cervical cancer, esophageal cancer, gastric cancer, hepatocellular carcinoma, merkel cell carcinoma, primary mediastinal large B-cell lymphoma, renal cell carcinoma, small cell lung cancer, MSI-H/dMMR cancer or unresectable or metastatic tumor mutational burden-high (TMB-H) [≥ 10 mutations/megabase (mut/Mb)] solid tumors will be eligible for the trial.

5.1.2 Subject Inclusion Criteria

Subjects must meet all the following inclusion criteria in order to be eligible for participation in this trial:

- Female or male aged ≥ 18 years on the day of informed consent signing;
- Has histologically confirmed metastatic melanoma that is treatment naïve or has relapsed after or is refractory to ipilimumab or BRAF inhibitor (if *BRAF* mutation positive),
OR
histologically confirmed metastatic NSCLC that has high PD-L1 expression (TPS $\geq 50\%$) with no *EGFR* or *ALK* genomic tumor aberrations or histologically confirmed metastatic NSCLC that is PD-L1 positive (TPS $\geq 1\%$) and has progressed on or after platinum containing therapy (subjects with NSCLC harboring *EGFR/ALK* genomic aberrations must have received an FDA-approved targeted therapy for these aberrations)
OR
histologically confirmed HNSCC that has relapsed after or is refractory to platinum-containing chemotherapy,
OR
histologically confirmed cHL that has relapsed after three or more lines of therapy or is refractory to treatment
OR
histologically confirmed locally advanced or metastatic urothelial carcinoma that is not eligible for platinum-containing chemotherapy or that has relapsed after or is refractory to platinum-containing chemotherapy
OR
histologically confirmed advanced, PD-L1–positive cervical cancer with disease progression on or after chemotherapy that is not eligible for platinum-containing chemotherapy or that has relapsed after or is refractory to platinum-containing chemotherapy
OR
histologically confirmed recurrent, locally advanced or metastatic, squamous cell carcinoma of the esophagus (ESCC) whose tumors express PD-L1 (Combined Positive Score [CPS] ≥ 10), as determined by an FDA-approved test, with disease progression after one or more prior lines of systemic therapy.
OR
histologically confirmed recurrent, locally advanced or metastatic Gastric Cancer , with disease progression on or after two or more systemic therapies, including fluoropyrimidine- and platinum-containing chemotherapy and, if appropriate, HER2/neu-targeted therapy, and whose tumors express programmed death-ligand 1 (PD-L1), as determined by an FDA-approved test.

OR
histologically confirmed hepatocellular carcinoma (HCC) who have been previously treated with sorafenib. recurrent locally advanced or metastatic MCC who had not received prior systemic therapy for their advanced disease. OR

histologically confirmed recurrent, locally advanced or metastatic Merkel Cell Carcinoma (MCC) who had not received prior systemic therapy for their advanced disease.

OR

histologically confirmed advanced renal cell carcinoma (RCC) first-line treatment.

OR

histologically confirmed metastatic small cell lung cancer (SCLC) with disease progression on or after platinum-based chemotherapy and at least one other prior line of therapy.

OR

histologically confirmed refractory primary mediastinal large B-cell lymphoma (PMBCL), who have relapsed after two or more prior lines of therapy.

OR

MSI-H or dMMR unresectable or metastatic cancer that has relapsed after prior treatment and has no satisfactory alternative treatment options;

OR

adult patients with unresectable or metastatic tumor mutational burden-high (TMB-H) [≥ 10 mutations/megabase (mut/Mb)] solid tumors;

- Measurable disease based on RECIST 1.1;
- Eastern Cooperative Oncology Group (ECOG) performance status of 0–2 (see Section 11.3);
- Life expectancy ≥ 6 months;
- Adequate organ function as defined in Table 4. All screening labs should be performed within 28 days of treatment initiation.

Table 4

System	Laboratory Value
Hematological	
Absolute neutrophil count (ANC)	$\geq 1,500/\text{mm}^3$
Platelets	$\geq 100,000/\text{mm}^3$
Hemoglobin	≥ 9 g/dL (transfusion permitted)
Renal	
Serum creatinine OR Measured or calculated ^a creatinine clearance (CrCl) (glomerular filtration rate can be used in place of creatinine or CrCl)	≤ 1.5 X upper limit of normal (ULN) OR ≥ 60 mL/min for subject with creatinine levels > 1.5 X institutional ULN
Hepatic	
Serum total bilirubin	≤ 1.5 X ULN OR Direct bilirubin \leq ULN for subjects with total bilirubin levels > 1.5 ULN
ALT and AST	≤ 2.5 X ULN OR ≤ 5 X ULN for subjects with liver metastases
Albumin	≥ 2.5 mg/dL
Coagulation	
International normalized ratio (INR) or prothrombin time (PT)	≤ 1.5 X ULN unless subject is receiving anticoagulant therapy as long as PT or PTT is within therapeutic range of intended use of anticoagulants
Activated partial thromboplastin time (aPTT)	≤ 1.5 X ULN unless subject is receiving anticoagulant therapy as long as PT or PTT is within therapeutic range of intended use of anticoagulants

^a CrCl should be calculated per institutional standard.

- Cardiac ejection fraction of $\geq 45\%$;
- Female subjects of childbearing potential should have a negative serum pregnancy (β -human chorionic gonadotropin [β -HCG]) within 7 days prior to receiving the first dose of trial treatment and should not be lactating;
- Female subjects of childbearing potential must be willing to use an adequate method of contraception as outlined in Section 5.5.2 — Contraception for the course of the trial through 120 days after the last dose of trial treatment;
- Male subjects of childbearing potential must be willing to use an adequate method of contraception as outlined in Section 5.5.2 — Contraception for the course of the trial through 120 days after the last dose of trial treatment;
- Willing and able to provide written informed consent/assent for the trial.

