1.1.2.10 Pembrolizumab and TMB-H solid tumors

Efficacy of pembrolizumab was investigated in a prospectively-planned retrospective analysis of 10 cohorts of patients with various previously treated unresectable or metastatic TMB-H solid tumors enrolled in a multicenter, non-randomized, open-label trial, KEYNOTE-158 (NCT02628067). Patients received pembrolizumab 200 mg intravenously every 3 weeks until unacceptable toxicity or documented disease progression. The main efficacy outcome measures were overall response rate (ORR) and duration of response (DoR) in patients who have received at least one dose of pembrolizumab as assessed by blinded independent central review according to RECIST v1.1, modified to follow a maximum of 10 target lesions and a maximum of 5 target lesions per organ. A total of 102 patients (13%) had tumors identified as TMB-H, defined as TMB ≥ 10 mut/Mb. The ORR for these patients was 29% (95% CI: 21,39), with a 4% complete response rate and 25% partial response rate. The median DoR was not reached, with 57% of patients having response durations ≥ 12 months and 50% of patients having response durations ≥ 24 months. Adverse reactions occurring in patients with TMB-H cancer enrolled in KEYNOTE-158 were similar to those occurring in patients with other solid tumors who received pembrolizumab as a single agent.

The most common adverse reactions to pembrolizumab are fatigue, musculoskeletal pain, decreased appetite, pruritus, diarrhea, nausea, rash, pyrexia, cough, dyspnea, constipation, pain, and abdominal pain. Pembrolizumab is associated with immune-mediated side effects, including pneumonitis, colitis, hepatitis, endocrinopathies, nephritis, and skin adverse reactions.

The recommended pembrolizumab dosage regimen for TMB-H solid tumors is 200 mg every 3 weeks or 400 mg every 6 weeks for adults. The FDA also approved the FoundationOneCDx assay (Foundation Medicine, Inc.) as a companion diagnostic for pembrolizumab.

Table 1. MSI-H/dMMR Trials²⁸

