1.2 Rationale

1.2.1 Rationale for the Trial and Selected Subject Population

Pembrolizumab has demonstrated significant clinical activity in patients with melanoma, NSCLC, HNSCC, cHL, urothelial carcinoma, cervical cancer, esophageal cancer, gastric cancer, hepatocellular carcinoma, merkel cell carcinoma, primary mediastinal large B-cell lymphoma, renal cell carcinoma, small cell lung cancer, MSI-H/dMMR cancer, and for the treatment of adult and pediatric patients with unresectable or metastatic tumor mutational burden-high (TMB-H) [≥ 10 mutations/megabase (mut/Mb)] solid tumors, as determined by an FDA-approved test, that have progressed following prior treatment and who have no satisfactory alternative treatment options.. However, a significant proportion of these patients do not respond to or progress after anti-PD-1 therapy, highlighting the need for novel strategies to optimize the efficacy of this therapy. The TIME has emerged as a critical determinant of immune checkpoint inhibitor response, with responses correlated with an immunologically active T-cell-inflamed microenvironment.³⁸ We and others have shown that NOS induces immune dysfunction in the tumor microenvironment.⁴²⁻⁴⁴ Therefore, we hypothesize that NOS inhibition, by targeting the immunosuppressive tumor microenvironment, will reverse resistance to PD-1 blockade and enhance response rates to pembrolizumab in patients with melanoma, NSCLC, HNSCC, cHL, urothelial carcinoma, cervical cancer, esophageal cancer, gastric cancer, hepatocellular carcinoma, merkel cell carcinoma, primary mediastinal large B-cell lymphoma, renal cell carcinoma, small cell lung cancer, MSI-H/dMMR cancer or patients with unresectable or metastatic tumor mutational burden-high (TMB-H) [≥ 10 mutations/megabase (mut/Mb)] solid tumors. We will increase the number of subjects enrolled to 20 subjects to allow for Screen-Fails/withdrawals/deaths. The protocol study population will remain at 12 evaluable subjects.

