 - Has known active central nervous system metastases and/or carcinomatous meningitis. Subjects with previously treated brain metastases may participate provided they are stable (without evidence of progression by imaging for at least 4 weeks prior to the first dose of trial treatment and any neurologic symptoms have returned to baseline), have no evidence of new or enlarging brain metastases, and are not using steroids for at least 7 days prior to trial treatment. This exception does not include carcinomatous meningitis which is excluded regardless of clinical stability;
 - Has active autoimmune disease that has required systemic treatment in the past 2 years (i.e., with use of disease-modifying agents, corticosteroids or immunosuppressive drugs). Replacement therapy (e.g., thyroxine, insulin, or physiologic corticosteroid replacement therapy for adrenal or pituitary insufficiency, etc.) is not considered a form of systemic treatment;
 - History of non-infectious pneumonitis that required steroids or current pneumonitis;
 - Has an active infection requiring systemic therapy;
 - History or current evidence of any condition, therapy, or laboratory abnormality that might confound the results of the trial, interfere with the subject's participation for the full duration of the trial, or is not in the best interest of the subject to participate, in the opinion of the treating investigator;
 - Known psychiatric or substance abuse disorders that would interfere with cooperation with the requirements of the trial;
 - Is pregnant or breastfeeding, or expecting to conceive a child within the projected duration of the trial, starting with the prescreening or screening visit through 120 days after the last dose of trial treatment;
 - Received prior therapy with an anti-PD-1, anti-PD-L1, or anti-PD-L2 agent;
 - Known history of human immunodeficiency virus (HIV) (HIV 1/2 antibodies);
 - Has known active hepatitis B (e.g., HBsAg reactive) or hepatitis C (e.g., HCV RNA [qualitative] is detected);
 - Received a live vaccine within 30 days of planned start of the trial treatment.
Note: Seasonal influenza vaccines for injection are generally inactivated flu vaccines and are allowed; however, intranasal influenza vaccines (e.g., Flu-Mist®) are live attenuated vaccines and are not allowed;
 - Unwilling or unable to comply with the trial protocol.

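### The TMB-H inclusion line in 5.1.2 carries no prior-treatment or no-alternative condition, so an untreated solid tumor that fails its tumor-specific line can enter through it

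*Combined protocol and SAP*

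**What the plan says.** Section 5.1.2 (Subject Inclusion Criteria) lists the qualifying diseases as alternatives joined by OR. The last alternative is "adult patients with unresectable or metastatic tumor mutational burden-high (TMB-H") solid tumors at or above 10 mut/Mb. It has no condition on prior therapy, progression, remaining options or the test used.

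The alternative just before it reads "MSI-H or dMMR unresectable or metastatic cancer that has relapsed after prior treatment and has no satisfactory alternative treatment options".

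Two background passages describe the TMB-H population more narrowly:

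- Section 1.2.1, opening sentence: TMB-H solid tumors identified by an FDA-approved test "that have progressed following prior treatment and who have no satisfactory alternative treatment options".
- Section 1.1.2.10: the supporting analysis covered "10 cohorts of patients with various previously treated unresectable or metastatic TMB-H solid tumors".

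Several tumor-specific lines in 5.1.2 set explicit prior-therapy requirements. The HNSCC line is "histologically confirmed HNSCC that has relapsed after or is refractory to platinum-containing chemotherapy", and the small cell line is "metastatic small cell lung cancer (SCLC) with disease progression on or after platinum-based chemotherapy and at least one other prior line of therapy".

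The one general criterion that bears on the matter is in 5.1.3. It excludes a subject with a history or current evidence of any condition, therapy or laboratory abnormality that "is not in the best interest of the subject to participate, in the opinion of the treating investigator".

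**The concern.** When eligibility lines are alternatives, the least restrictive one sets the effective threshold for everyone who can meet it. A TMB-H line without a prior-therapy condition therefore opens a second route for patients whom the tumor-specific lines were written to keep out until they have had certain treatments.

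The main stake is subject protection. A patient who has not yet had the therapy that the protocol itself requires for that tumor could enter a dose-finding trial of a combination whose MTD is not yet known. Section 5.3.2 then bars other systemic anticancer treatment, including targeted agents, while the patient is on trial.

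A lesser stake is interpretation. The response data cited for TMB-H tumors (ORR 29%, section 1.1.2.10) come from previously treated patients, and the documents give no corresponding figure for untreated ones.

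**Working it through.** No arithmetic applies. The check compares texts and then follows the OR logic.

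**Step 1. Conditions attached to the two biomarker-defined populations.**

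| Place | Progressed or relapsed after prior treatment | No satisfactory alternative | FDA-approved test |
|---|---|---|---|
| 1.2.1, opening sentence, TMB-H | yes | yes | yes |
| 1.1.2.10, cited TMB-H data | previously treated | not stated | not stated as an entry condition |
| 5.1.2, TMB-H line | no | no | no |
| 5.1.2, MSI-H/dMMR line | yes | yes | no |

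**Step 2. Does another criterion supply the missing conditions?** The other inclusion items concern age, measurable disease, performance status, life expectancy, organ and cardiac function, pregnancy and contraception, and consent. The exclusions in 5.1.3 cover washout, prior PD-1/PD-L1/PD-L2 agents, comorbidity and the best-interest item. None requires earlier therapy, progression or exhaustion of alternatives. The best-interest item is discretionary.

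**Step 3. Which lines can be bypassed on prior therapy?**

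| Line in 5.1.2 | Prior-therapy requirement | Effect of the TMB-H line |
|---|---|---|
| NSCLC, TPS at least 1% | progression on or after platinum; targeted therapy first if EGFR/ALK-aberrant | bypassed |
| HNSCC | relapsed after or refractory to platinum | bypassed |
| SCLC | platinum and at least one other line | bypassed |
| Gastric | two or more systemic therapies | bypassed |
| Melanoma; NSCLC with TPS at least 50% and no EGFR/ALK aberration; MCC; RCC | untreated patients already admitted | no prior-therapy condition to bypass |
| cHL; PMBCL | set by line | unaffected, because the TMB-H line covers solid tumors only |

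**Step 4. Worked case.** Take metastatic NSCLC with an EGFR aberration, untreated, TMB of 10 mut/Mb or more. The TPS at least 50% route is closed because it requires no such aberration. The TPS at least 1% route is closed because neither platinum nor targeted therapy has been given. The TMB-H line is met. If the general criteria are met, the patient is eligible, although the NSCLC line says that targeted therapy must have come first.

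**Step 5. What does not change.** The primary endpoint is the MTD (3.1). The CRM settings, the 12 subjects and the operating characteristics in Table 9 (8.0) take no input from this eligibility line.

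**The case against.** The strongest reply is that the operative text is consistent and only one background sentence differs. The conditions appear once, in the opening sentence of 1.2.1. That sentence reports where pembrolizumab has shown activity, and it extends to pediatric patients, whom this trial does not take. The hypothesis sentence in the same section, the objectives (2.1, 2.2), the design (4.1), the entry diagnosis (5.1.1) and the statistics section (8.0) all name TMB-H without conditions.

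Part of this stands. A reader might infer that the inclusion line violates the trial's defined population. The documents do not go that far, because the opening sentence of 1.2.1 does not define who is enrolled. But the bare mentions elsewhere do not show that a broader population was chosen either: the same lists name HNSCC, SCLC, gastric cancer and MSI-H/dMMR without their conditions. Section 5.1.2 is where conditions are set. It sets them for MSI-H/dMMR and not for TMB-H, and no passage explains the difference.

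Three further replies succeed in narrowing the point:

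- **Mixing of treated and untreated subjects.** One might infer that this line spoils the antitumor-activity endpoint. Untreated patients already enter through the melanoma, high-TPS NSCLC, MCC and RCC lines, so the mix would remain after any correction. Antitumor activity is a secondary endpoint, and section 8.0 sets no response hypothesis for it.
- **Size.** One might take the 102 patients (13%) in 1.1.2.10 to mean that about 1 in 8 patients who fail their own line could enter. That share comes from previously treated cohorts of another trial and cannot be carried over to untreated patients here. Table 6 schedules no TMB test, so within the scheduled procedures the route depends on a TMB result obtained elsewhere.
- **Test requirement.** The missing FDA-approved test is a minor matter. The NSCLC, cervical and MSI-H/dMMR lines do not require one either.

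The best-interest exclusion may keep out an individual patient. It does not replace a written criterion.

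**Conclusion.** The point holds as a gap in eligibility wording. As written, 5.1.2 lets a patient with an untreated TMB-H solid tumor enter despite failing an explicit prior-therapy requirement for that tumor. Both the description in 1.2.1 and the neighboring MSI-H/dMMR line suggest that the missing conditions were left out in drafting, although the documents do not prove it.

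The effect is confined to solid tumors whose own line demands earlier therapy. Its frequency cannot be estimated from the documents. The dose-finding design and its operating characteristics are untouched. The conclusion rests on two readings: that OR means any one line suffices, and that no criterion outside 5.1.2 and 5.1.3 governs entry. This is a cheap improvement that should be made, not a flaw that invalidates the plan.

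**What to change.** Reconcile 1.2.1 with the TMB-H line of 5.1.2 in one of two ways:

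1. Carry the prior-treatment and no-alternative conditions already written in 1.2.1 into the TMB-H line, as the MSI-H/dMMR line does.
2. If the broader population is intended, justify it in 1.2.1 and state in 5.1.2 that the TMB-H line does not override the prior-therapy requirements of the tumor-specific lines.

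Section 5.1.1 needs no change, since it lists diagnoses without prior-therapy conditions for every tumor. For the same reason the objectives, design and statistics sections can stay as they are.

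The first option costs a one-sentence amendment and a slightly narrower eligible pool. The second adds a short justification in 1.2.1. Neither requires a change to the sample size, the CRM or Table 9.

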5.1.3 Subject Exclusion Criteria

Subjects meeting any of the following exclusion criteria must be excluded from participating in the trial:

- History of poorly controlled hypertension (defined as systolic blood pressure > 150 mmHg). Subjects with medication-controlled hypertension are allowed provided they have been on their current medication for at least 4 weeks prior to Cycle 1, Day 1;
- History of New York Heart Association class III or greater cardiac disease (see Section 11.4);
- History of myocardial infarction, stroke, ventricular arrhythmia, or symptomatic conduction abnormality within the past 12 months;
- History of congenital QT prolongation;
- Absolute corrected QT interval of > 480 msec in the presence of potassium > 4.0 mEq/L and magnesium > 1.8 mg/dL;
- Currently participating and receiving study therapy or has participated in a study of an investigational agent and received study therapy or used an investigational device within 4 weeks of the first dose of the trial treatment;
- Concurrent use of medications that interact with nitrate/nitrites (see Section 11.5);
- Concurrent use of any complementary or alternative medicines;
- Has a diagnosis of immunodeficiency or is receiving systemic steroid therapy or any other form of immunosuppressive therapy within 7 days prior to the first dose of trial treatment;
- Known history of active tuberculosis (Bacillus Tuberculosis);
- Hypersensitivity to L-NMMA, pembrolizumab, or any of their excipients;
- Has had a prior anticancer monoclonal antibody within 4 weeks prior to study Day 1 or who has not recovered (i.e., \leq Grade 1 or at baseline) from AEs due to agents administered more than 4 weeks earlier;
- Has had prior chemotherapy, targeted small molecule therapy, or radiation therapy within 4 weeks prior to study Day 1 or who has not recovered (i.e., \leq Grade 1 or at baseline) from AEs due to a previously administered agent.

- Note: Subjects with \leq Grade 2 neuropathy are an exception to this criterion and may qualify for the trial.
 - Note: If subject received major surgery, they must have recovered adequately from the toxicity and/or complications from the intervention prior to starting the trial treatment.
- Has a known additional malignancy that is progressing or requires active treatment. Exceptions include basal cell carcinoma of the skin or squamous cell carcinoma of the skin that has undergone potentially curative therapy or in situ cervical cancer.
 - Has known active central nervous system metastases and/or carcinomatous meningitis. Subjects with previously treated brain metastases may participate provided they are stable (without evidence of progression by imaging for at least 4 weeks prior to the first dose of trial treatment and any neurologic symptoms have returned to baseline), have no evidence of new or enlarging brain metastases, and are not using steroids for at least 7 days prior to trial treatment. This exception does not include carcinomatous meningitis which is excluded regardless of clinical stability;
 - Has active autoimmune disease that has required systemic treatment in the past 2 years (i.e., with use of disease-modifying agents, corticosteroids or immunosuppressive drugs). Replacement therapy (e.g., thyroxine, insulin, or physiologic corticosteroid replacement therapy for adrenal or pituitary insufficiency, etc.) is not considered a form of systemic treatment;
 - History of non-infectious pneumonitis that required steroids or current pneumonitis;
 - Has an active infection requiring systemic therapy;
 - History or current evidence of any condition, therapy, or laboratory abnormality that might confound the results of the trial, interfere with the subject's participation for the full duration of the trial, or is not in the best interest of the subject to participate, in the opinion of the treating investigator;
 - Known psychiatric or substance abuse disorders that would interfere with cooperation with the requirements of the trial;
 - Is pregnant or breastfeeding, or expecting to conceive a child within the projected duration of the trial, starting with the prescreening or screening visit through 120 days after the last dose of trial treatment;
 - Received prior therapy with an anti-PD-1, anti-PD-L1, or anti-PD-L2 agent;
 - Known history of human immunodeficiency virus (HIV) (HIV 1/2 antibodies);
 - Has known active hepatitis B (e.g., HBsAg reactive) or hepatitis C (e.g., HCV RNA [qualitative] is detected);
 - Received a live vaccine within 30 days of planned start of the trial treatment.
Note: Seasonal influenza vaccines for injection are generally inactivated flu vaccines and are allowed; however, intranasal influenza vaccines (e.g., Flu-Mist®) are live attenuated vaccines and are not allowed;
 - Unwilling or unable to comply with the trial protocol.

